5. MATERIALS AND METHODS

5.1. Study area

The study will be conducted at sites across several sites in Ethiopia to obtain sufficient enrolment and spanning different transmission settings based on epidemiological data provided by the Federal Ministry of Health. The study sites selected are Chisabay, Hamusit and Andasa Health centers; northwest Ethiopia, from southwest Ethiopia; Bonga area (Uffa Health Center and Bonga (GebreTsadik Shawo) General Hospital) and one site from Gambela (Lare Health center); in which some are sites where preliminary data were gathered. In Ethiopia, malaria is characterized by its seasonality where the peak transmission season is from October to December with a second peak in June. *P. falciparum* and *P. vivax* are the predominant species in the area [22]. Residents often live in non-substantive accommodation and despite a scale up in preventative measures in 2005 including ITN distribution, they are at risk of malaria.

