5.7.4. Loop-mediated isothermal amplification (LAMP)

Since patients testing positive by LAMP will be treated for malaria, a CE-marked test (approved for human use in Europe) will be used to diagnose patients. We will use the Meridien Biosciences, Illumigene Malaria M kit (Cincinatti, USA) and Eiken LoopAMP Malaria (Human Diagnostics, Wiesbaden, Germany). The test will be conducted exactly according to manufacturer's recommendations. The tests are both run to detect *P. falciparum* and *P. vivax*. A third investigational LAMP test (ELUCIDx, Calgary, Canada) will be run only for data gathering and method validation purposes.

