Pregnant women who do not consent to participate in the study will be tested for malaria using standard Giemsa microscopy, ensuring that they receive prompt treatment, as per Ethiopian national guidelines. Pregnant women who are severely unwell requiring admission to the health center for monitoring or referred to a hospital will be excluded from the study. Only CE-marked commercially available diagnostic tests for LAMP (Meridien Biosciences, Illumigene Malaria M kit, Cincinatti, USA) will be used in this study. These kits are able to identify both *P. falciparum* and *P. vivax* to the species level. Treatment will be according to national guidelines for symptomatic and asymptomatic women positive for *Plasmodium*. Quinine has been widely used for MiP treatment. The main adverse effect of quinine are cinchonism (with tinnitus (38%-85%), vomiting, dizziness, nausea and anorexia), quinine related hypoglycemia (17%) and QT prolongation (1%) [23]. Abortion risk is considered as very low for quinine [24] at the normal dosage.

Artemisinin derivatives (in combination with partner drug such as lumefantrine) showed similar profiles in terms of stillbirth, congenital abnormalities and risk of miscarriage in women exposed to ACT during pregnancy compared to standard intermittent preventive treatment (IPT) for malaria [23]. Despite animal preclinical studies highlighting a risk of embryotoxicity and teratogenicity (musculoskeletal/cardiovascular defects) [25], a recent meta-analysis study did not show a difference in pregnant women treated with ACT compared to quinine, even in the embryo sensitive University of Calgary Conjoint Health Research Ethics Board (CHREB) number: REB17 – 1335 ClinicalTrials.gov Identifier: NCT03754322 v.1.1 29 March 2020

period (6-12 weeks of gestational age) [26]. Two studies report ECG monitoring of pregnant women treated by artemether lumefantrine [27,28] and showed a QT prolongation in 2% of treated women. Several studies have reported the safety of artemether lumefantrine during the first trimester of pregnancy in 1693 women, and no increase in miscarriage or congenital abnormalities where observed compared to standard of care [29–32]. Recently, the PREGACT trial compared four artesunate combined therapy in the second and third trimester of pregnancy in women positive for *P. falciparum* infection regardless of symptoms. No differences were observed in terms of treatment associated negative birth outcomes [33].

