Regarding chloroquine, a cohort of 169 pregnant women treated by chloroquine in non-malaria endemic area did not show newborn abnormalities compared to placebo [34]. Recently, a study conducted in Malawi to evaluate the use of chloroquine for intermittent preventive treatment did not show any adverse effect in the 600 treated women compared to the standard of care IPT (sulfadoxine pyrimethamine) [35].

In regards of the recent literature and publications related to quinine, artemether lumefantrine and chloroquine during pregnancy, there is no major risk for treatment of women presenting asymptomatic *Plasmodium* spp infection. Importantly, *Plasmodium* spp infection, even asymptomatic and submicroscopic, has impact on birth outcomes.

Asymptomatic malaria is the presence of *Plasmodium* spp infection in peripheral blood in the absence of any symptom of the disease. During pregnancy, peripheral parasitemia are particularly low due to sequestration of infected erythrocytes in the placenta villosities [36,37]. The sequestration of the parasite in the placenta originates the negative birth outcomes associated with MiP : low birth weight, maternal anemia, abortion and stillbirth [38]. Estimation recall that 20% of stillbirth and 11% of all newborn death are direct consequences of MiP [39]. Both *P. falciparum* and *P. vivax* induce adverse pregnancy outcome. *P. falciparum* pathogenicity in MiP is well described [37,40] while the pathophysiology of *P. vivax* infection during pregnancy needs yet to be elucidated [41,42].

It is clearly demonstrated that pregnant women presenting asymptomatic or submicroscopic *Plasmodium* infection present more anemia than uninfected women [43]. A recent longitudinal study combining *Plasmodium* peripheral detection and placenta histology at delivery showed that

even women with only submicroscopic infection have an increased risk of placental malaria compared to women without any parasitemia [44].

[figure not shown]
For the above-mentioned reason, *Plasmodium* infection, even asymptomatic, present a risk for the mother health and fetal development.

Expectant mother safety is a priority during the LAMPREG trial. After *Plasmodium* spp infection diagnostic, final treatment choice will be at the discretion of the physician assessing the patient. Any pre-existing condition will be taken in consideration.

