data collection", "lost to follow up". This will be presented in CONSORT diagram format rather than as a table, with numbers and reasons for withdrawal and/or exclusion from the analysis given at each stage. The numbers (with reasons) of losses to follow-up (dropouts and withdrawals) over the course of the trial will be summarized by treatment arm.

5. Population and subgroup to be analyzed

Intention-to-treat (ITT): All randomized study subjects. This will be the primary population for the analysis.

Per Protocol (PP): All randomized study subjects completing the whole study period (complete cases). For a specific analysis, study subjects with missing data on any of the variables in the model will be excluded from the analysis. Analyses of this population is seen as a sensitivity analysis to investigate whether conclusions are sensitive to assumptions regarding the pattern of missing data

We will analyze independently the following subgroups (Both ITT and PP populations):

- a. Primiparous mother
- b. **Asymptomatic malaria**: women who did not present symptom at any ANC visit but were detected positive for *Plasmodium* spp infection by any diagnostic method.
- c. **Sub microscopic malaria**: any women diagnosed positive for malaria by molecular method (LAMP or post hoc gold standard RT-qPCR)
- d. Malaria species identified: *P. falciparum*, *P. vivax* and mixed infections (3 subgroups)
- e. Women presenting positive malaria testing in placental blood at delivery
- f. Women from newborn with Low Birth Weight

6. Baseline patient characteristics

Expectant women will be described with respect to age, parity, gestity, gestational age, history of malaria, pregnancy complication, both overall and separately for the two randomized groups. These data will be summarized in a table.

Section 6: Analysis

1. Outcome definition

Primary study outcomes are related to newborn health: fetal anemia (hemoglobin <12.5 g/dL), mean birthweight, low birthweight (<2500 g), mean gestational age, preterm delivery (<37 weeks' gestation), mean birthweight for gestational age (Z scores), small for gestational age, fetal loss (spontaneous abortion at <28 weeks' gestation or stillbirth), and the composite outcomes of adverse livebirth (preterm, low

birthweight, or small for gestational age) and adverse pregnancy (adverse livebirth or fetal loss). Mortality outcomes included neonatal, perinatal, and mortality up to age 4 weeks.

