Secondary outcomes were signs of placental malaria infection at delivery, defined as a composite of maternal malaria (detection of infection in peripheral blood with post hoc gold standard testing) or placental malaria (detection of infection in placental blood with microscopy, molecular testing for active infection, or malaria pigment in blood smear monocytes for signs of past infection)

Secondary outcomes include maternal anemia (any: hemoglobin level <11 g/dL; moderate: hemoglobin level <9 g/dL) during each ANC visit and at delivery. We will use the categories "no anemia", "mild anemia", "moderate anemia" and "severe anemia" using the reference values for each pregnancy trimester. Values will be disaggregated according to gestational age.

Secondary outcomes during pregnancy comprised maternal malaria, detected with any method and by each method separately. This outcome was further stratified by patent infection (positive microscopy or malaria rapid diagnostic test) and sub-patent infection (negative microscopy and malaria rapid diagnostic test and positive LAMP–PCR). Morbidity outcomes assessed during pregnancy comprised clinical malaria (documented or history of fever plus positive malaria rapid diagnostic test or microscopy) and unscheduled clinic visits for any reason and for all reasons unrelated to malaria.

2. Analysis methods

Mean values of quantitative variables will be compared using a two-sided t-test with a significance of p < 0.05. We will use a negative binomial model to assess the effect of asymptomatic malaria screening using the number of (i) both microscopic and submicroscopic and (ii) submicroscopic *P. falciparum* infections occurring during pregnancy with an adjustment for the confounding variables. Multiple test correction will be implemented.

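### The only model named for screening's effect on infection counts appears limited to P. falciparum, while the trial tests for and treats any Plasmodium; no between-arm model covers all-species or P. vivax counts

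*SAP*

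**What the plan says.** SAP Section 6.2 (Analysis methods) begins: "We will use a negative binomial model to assess the effect of asymptomatic malaria screening using the number of (i) both microscopic and submicroscopic". The sentence goes on to item (ii), "submicroscopic *P. falciparum* infections occurring during pregnancy with an adjustment for the confounding variables". No other species is named there and no reason is given for naming one. This is the only model in the SAP whose stated purpose is to measure what screening does to the number of infections.

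The protocol takes a wider view of the target:

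- Section 5.1, on the study area: "P. falciparum* and *P. vivax* are the predominant species in the area".
- Section 5.7.4, on the two commercial LAMP kits: "The tests are both run to detect *P. falciparum* and *P. vivax".
- Section 5.12, on treatment: "Treatment will be according to national guidelines for symptomatic and asymptomatic women positive for *Plasmodium".
- Section 5.12, on harm: "Both *P. falciparum* and *P. vivax* induce adverse pregnancy outcome".

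Elsewhere the SAP is not confined to one species. Section 6.1 states: "Secondary outcomes during pregnancy comprised maternal malaria, detected with any method and by each method separately", divided into patent and sub-patent infection with no species limit. Section 5.5 lists as a subgroup: "Malaria species identified: *P. falciparum*, *P. vivax* and mixed infections (3 subgroups". The log-binomial and quantile regressions in Section 6.2 refer to malaria status or malaria infection in general.

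**The concern.** The strategy under test is screening for, and treating, Plasmodium infection. A count restricted to P. falciparum answers a narrower question. The two answers can differ if screening and treatment affect the species differently, for example if P. vivax infections recur more often after treatment. Whether that happens here is not known from the documents.

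At stake is the infection result that would explain any effect on birth outcomes. A ratio for one species could be read as the ratio for the strategy. Infections averted in the other species would not be counted, and the estimate would rest on fewer events. An unclear species scope also leaves room to settle it after the data are seen.

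**Working it through.** **1. Which counts are restricted.** Items (i) and (ii) share one closing noun phrase. Without the words naming P. falciparum infections, item (i) has no noun, so the natural reading applies the restriction to both. The alternative attaches it to item (ii) only and leaves (i) open to all species. Even then the submicroscopic count, which is the category LAMP is meant to add, covers one species. Counts (i) and (ii) would also differ in species as well as in detectability, so they could not be compared with each other.

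**2. Whether another analysis fills the gap.**

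| Planned item | Species scope | Gives an arm effect on all-species or P. vivax counts? |
|---|---|---|
| Negative binomial model (SAP 6.2) | P. falciparum, at least for (ii) | Not for P. vivax; for all species only if (i) is read as unrestricted |
| Maternal malaria, patent and sub-patent (SAP 6.1) | Any | Outcome defined, but no between-arm model named |
| Log-binomial and quantile regression (SAP 6.2) | Any | No: infection is the exposure and birth outcome the response |
| Species subgroups (SAP 5.5) | Three groups | No: membership depends on a positive test after randomisation |

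The last row matters. Looking within women already positive for P. vivax cannot show whether screening changed how many P. vivax infections occurred.

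**3. Effect on the rate ratio (illustration).** The SAP states no expected rate, ratio or precision for this model, so there is no planned figure to reproduce. Assume P. vivax is a share v of infections in the standard-of-care arm, the P. falciparum rate ratio is 0.60, the P. vivax rate ratio is R, and each infection counts under one species.

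All-species ratio = (1 − v) × 0.60 + v × R.

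Share of averted infections missed by a P. falciparum count = v(1 − R) / [(1 − v) × 0.40 + v(1 − R)].

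| R | All-species ratio, v = 0.1 to 0.5 | Averted infections missed |
|---|---|---|
| 0.4 | 0.58 to 0.50 | 14% to 60% |
| 0.6 | 0.60 throughout | 10% to 50% |
| 0.8 | 0.62 to 0.70 | 5% to 33% |
| 1.0 | 0.64 to 0.80 | 0% |

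Example, v = 0.5 and R = 0.8: ratio = 0.30 + 0.40 = 0.70; missed = 0.10 / (0.20 + 0.10) = 33%.

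**4. Effect on precision (illustration).** Under a negative binomial model each arm contributes (1/m + k)/n to the variance of the log rate ratio, where m is the mean count and k the dispersion. If a share s of events is dropped from both arms and k stays the same, the standard error is multiplied by

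√{[1/((1 − s)m) + k] / [1/m + k]}.

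With k = 0 (Poisson) this becomes 1/√(1 − s), which is the upper limit for constant k: 1.12 at s = 0.2 and 1.41 at s = 0.5. With assumed m = 0.35 in both arms:

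- s = 0.2, k = 1: √(4.571/3.857) = 1.09; k = 2: √(5.571/4.857) = 1.07.
- s = 0.5, k = 1: √(6.714/3.857) = 1.32; k = 2: √(7.714/4.857) = 1.26.

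The loss is therefore about 7 to 9% at a 20% share and 26 to 32% at a 50% share. These figures compare standard errors for two different quantities.

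**The case against.** The strongest reply is that this is one secondary model in a plan that otherwise includes P. vivax. A reader might infer from the sentence that P. vivax is left out of the analysis altogether. The documents do not support that: maternal malaria is species-neutral, species subgroups are planned, and the birth-outcome models use any malaria. The gap is narrower, namely the absence of a specified comparison by arm.

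A reader might also infer that a P. falciparum count understates the strategy whenever screening works on both species. On the ratio scale that this model estimates, it does not: with equal effects the ratio stays at 0.60, and only the absolute number averted falls short. Nor should the Poisson inflation of 12 to 41% be taken as the expected loss of precision; it is an upper limit under constant dispersion.

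There is a partial rationale for the restriction. Protocol 5.12 regards the role of P. falciparum in pregnancy as well described and the mechanism for P. vivax as still unclear. That could justify a P. falciparum result. It does not justify having no all-species one, and the SAP does not make the argument.

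Two limits on the evidence stand. The SAP was written against protocol version 1.5, and the protocol supplied is version 1.1. The local-species statement cites a trend analysis from a place that is not among the listed sites.

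**Conclusion.** The point holds in a limited form. On its natural reading, the only model named for screening's effect on infection counts is confined to P. falciparum; on the more generous reading, the submicroscopic count still is. That is narrower than a strategy that tests for both species and treats any Plasmodium, and no other specified analysis compares all-species or P. vivax counts by arm.

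The consequence depends on how P. vivax responds. With a weaker response, the P. falciparum ratio overstates the strategy; with a stronger one, it understates it; with an equal one, the ratio is right but averted infections are under-counted and precision is lost. The ranges shown rest on assumed species shares, rate ratios, mean count and dispersion, because the documents give none of these for this model.

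It would be wrong to infer that the primary result is at risk. The low birth weight comparison and the sample size do not depend on this model. This is a worthwhile, inexpensive correction to a secondary analysis.

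**What to change.** In SAP Section 6.2, define both counts, total and submicroscopic, as infections with any Plasmodium species, compared by randomised arm, with a mixed infection counted once. State that infection is ascertained in the same way in both arms, using the qRT-PCR already planned on dried blood spots from all women (Protocol 5.7.2); LAMP results alone will not serve, since LAMP is used for screening only in the intervention arm. Report P. falciparum and P. vivax counts as pre-specified species-specific results under the multiple-test correction that Section 6.2 already promises. If the restriction to P. falciparum is intended, say so, say which count it covers, and give the reason.

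The cost is a sentence or two in the SAP and a few more secondary estimates. Design, sample size and clinical care do not change. The documents do not say whether the qRT-PCR assay reports species or whether spots are taken at every visit; the sponsor should confirm both. The model as written already needs molecular results in both arms to count submicroscopic infections, so the rewording adds little laboratory work if species is reported.

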5.8. Statistical Analysis Plan

Raw data will be entered in SPSS version 20 software and analyzed using STATA version 13. Mothers with twins will be excluded from the analysis of birth outcomes. The sensitivity, specificity and predictive values will be calculated for microscopy and LAMP versus a gold standard of PCR. Statistical analysis of epidemiological variables and malaria positivity will be determined using univariate binomial regression. Variables found to be statistically significant with initial analysis will then characterized through multivariate analysis regression analysis. Risk ratios for primary outcome variables for intervention against standard of care arm will be calculated. Subgroup analysis will be done for potential confounders, and to compare positivity by LAMP and microscopy in the intervention arm.

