LAMPREG study

Statistical Analysis Plan (SAP) statement

Version 1.0 – February 2021

Section 1: Administrative information

1. Title and Trial registration

Statistical analysis plan for the LAMP for Malaria in Pregnancy (LAMPREG) trial: "Active case detection and treatment of malaria in pregnancy using LAMP technology: A pragmatic randomized multi-Center diagnostic outcomes trial"

This trial is registered in clinicaltrial.gov: registration number NCT03754322

2. SAP version

Version: 1.0, Date: February 22nd, 2021

3. Protocol version

This document has been written based on information contained in the study protocol version 1.5, dated February 22^{nd} , 2021.

4. SAP revisions – revision history

Protocol version	Updated	SAP	Section	number	Description of and	Date changed
	version no.		changed		reason for change	
1.5	1.0		First SAP	version		February 22 nd , 2021

5. Roles and Responsibility – non signatory names and contribution

This SAP protocol was written and designed by

- [name], Post-Doctoral Associate, [name] Lab, The University of Calgary, AB, Canada
- [name], MD, AHRI, Addis Ababa, Ethiopia

• [name], MD, MSc, alumni [name] Lab, The University of Calgary, AB, Canada (current position, Microbiology Fellow, NIH, UK)

6. Roles and Responsibility – signatures

• [name], MD, PhD, PI of the LAMPREG study

Name	Name
Signature:	Signature:
Date:	Date:

Section 2: Introduction

1. Background and rationale

Malaria is an infectious disease transmitted by *Anopheles* mosquito. Pregnant women are particularly susceptible to adverse outcomes in terms of maternal and fetal health. Several prevention strategies are available to public health authorities to prevent malaria. These strategies are anti vectorial (bed nets, monitoring of stagnant water where mosquito larva bread), intermittent preventive treatment or repetitive screening during antenatal care (ANC). All the above mention strategy present limitations that impair their efficiency to prevent malaria-associated morbidity.

The LAMPREG trial aims to fill the knowledge gap by proposing an alternative systematic screening strategy using point of care (POC) compatible molecular biology techniques.

2. Objectives

Research hypothesis: The trial hypothesis is that enhanced LAMP-based malaria detection during ANC will lower the proportion of malaria-associated adverse outcomes (low birth weight, pregnancy loss, anemia). The proportion of Low Birth weight is the study primary outcome.

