The sample size calculation for this study is based on detecting a difference in the proportion of deliveries with a low birth weight (LBW), which was felt to be the most clinically important outcome variable. The prevalence of deliveries with a LBW in Ethiopia was estimated to be 17.3%. An alpha of 0.05 was selected with an allocation ratio of 3:1 in favor of the enhanced case detection arm. The study will be powered to detect an absolute difference in the proportion of deliveries with a LBW of 5%, so a proportion in the enhanced case detection arm of 12.3% compared to 17.3% in the standard of care arm. Using a continuity correction and an attrition rate of 20%, a total sample size of 2583 is required to achieve 80% power.

4. Framework

The LAMPREG trial aims to show the superiority of the intervention arm.

5. Statistical Interim analyses and stopping guidance

a. Two formal interim analysis are planned

- One formal statistical interim analysis is planned when 25% of the total inclusion target number (n = 646) is reached. This interim analysis will focus on the inclusion baseline data and the follow-up data available to date.
- Another formal statistical interim analysis is planed when 25% of the inclusion target reached the end of the protocol (28 days post-natal delivery). This analysis will be partial since post hoc gold standard molecular testing will not be available yet.
 - b. Adjustments planned of the significance level due to interim analysis

The prevalence of malaria in the study sites is paramount for the study outcome. Interim analysis will tailor this factor and decision of site closure or site initiation may be taken.

c. Details of guidelines for stopping the trial early

The LAMPREG trial interim results will be presented to an advisory board. LAMPREG is not a new interventional drug trial, and therefore unlikely to be subject to study termination. The Ethiopian NRERC ethical board waived the need of independent data monitoring and safety committee for LAMPREG.

6. Timing of final analysis

The final analysis of clinical data in the SOC *vs.* LAMP arm will be performed after the last follow up is completed, in a time frame of 6 months (secund semester of 2022), given that data entry is performed according to the protocol.

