Relative risk (RR) and corresponding 95% confidence intervals (CIs) of adverse birth outcomes and adverse pregnancy based on malaria status will be calculated using log-binomial regression with a log link function. We will use a multivariable quantile regression to further assess the effect of malaria infection on birth weight and gestational age at delivery. Multivariable models will be adjusted for co factors. Adjusters will be included in multivariable analyses based on an a priori hypothesized relationship with the outcome of interest and will be further considered if they had a p < 0.05 in bivariate analysis. No variables chosen as adjusters by substantive knowledge will be excluded based on the results of bivariate analysis. Ultimately, all variables included in the models, including those identified by bivariate screening, will be chosen among variables documented as risk factors for adverse birth outcomes and related to MIP.

3. Missing data

We will use simple imputation for missing covariates (<1%). For outcome variates, we will no implement imputation.

For birth weight, correction factors will be implemented for those collected outside of the study framework.

4. Additional analyses

N/A

5. Harms

6. Statistical software

The data entry is performed using RedCap. Data are exported in STATA and CSV format for analysis in Stata and R.

7. References

Statement references

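### SAP Section 6.2 gives no analysis of low birth weight by randomised arm: its only birth-outcome risk ratio is by malaria status, and no model names the parity strata used in randomisation

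*SAP*

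**What the plan says.** The intended comparison is stated in several places.

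- SAP Section 2.2: "The proportion of Low Birth weight is the study primary outcome".
- SAP Section 3.3 sizes the trial on LBW by arm: "so a proportion in the enhanced case detection arm of 12.3% compared to 17.3% in the standard of care arm".
- SAP Section 3.4: "The LAMPREG trial aims to show the superiority of the intervention arm".
- SAP Section 3.6 schedules a comparison of the arms after the last follow-up, beginning "The final analysis of clinical data in the SOC" and naming LAMP as the other arm.
- SAP Section 5.5, on the ITT population: "This will be the primary population for the analysis".
- Protocol Section 5.8 (v1.1): "Risk ratios for primary outcome variables for intervention against standard of care arm will be calculated".

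SAP Section 6.2, which should supply the method, lists four:

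1. a t-test for means of quantitative variables, with the groups not named;
2. a negative binomial model for the effect of screening, built on numbers of infections;
3. relative risks of "adverse birth outcomes and adverse pregnancy based on malaria status will be calculated using log-binomial regression with a log link function";
4. a quantile regression of birth weight and gestational age on malaria infection.

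Section 6.4 (additional analyses) is marked not applicable. SAP Section 3.2 has randomisation carried out at each health centre and stratified by three parity levels. Section 6.2 refers to confounders and co-factors without naming parity or centre.

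**The concern.** The SAP's methods section specifies a birth-outcome risk ratio, but for an exposure that was not randomised. Malaria status is acquired and detected after randomisation. Under Protocol Section 5.2, intervention women are tested by LAMP and by microscopy or RDT at every visit whether or not they have symptoms, whereas standard-of-care women are diagnosed by microscopy when symptomatic. A risk ratio by routinely detected status therefore compares groups formed differently in the two arms. Defining status by the later PCR testing would even out detection, but the comparison would still be observational.

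At stake is the pre-specification of the one comparison the trial is powered for. Section 6.2 fixes neither the estimator nor the covariates for LBW by arm. It also allows covariates to be considered on a bivariate p-value below 0.05, without saying that this route is closed to the between-arm model.

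**Working it through.** **1. What the sample size tests.** Inputs from SAP Sections 3.3 and 4.1: p1 = 0.173, p2 = 0.123, difference d = 0.05, two-sided alpha 0.05, power 80%, ratio k = 3, continuity correction, 20% attrition.

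- Pooled proportion: (0.173 + 3 × 0.123)/4 = 0.1355; variance 0.1355 × 0.8645 = 0.1171.
- Standard-of-care arm before correction: n = [1.960 × √((1 + 1/3) × 0.1171) + 0.842 × √(0.173 × 0.827 + 0.123 × 0.877/3)]² / 0.05² = (0.7746 + 0.3561)²/0.0025 = 511.4.
- Continuity correction: (n/4) × [1 + √(1 + 2(k+1)/(n·k·d))]² = 537.7, rounded up to 538.
- Total: 538 + 3 × 538 = 2152; 2152 × 1.2 = 2582.4, rounded up to 2583.

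The stated 2583 is reproduced exactly as a comparison of LBW proportions between randomised arms.

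**2. Section 6.2 set against that comparison.**

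| Method in Section 6.2 | Outcome | Contrast | LBW by arm? |
|---|---|---|---|
| t-test | means | not named | No: not a proportion |
| Negative binomial | built on infection counts | screening | No: not LBW |
| Log-binomial RR | adverse birth outcomes | malaria status | No: not by arm |
| Quantile regression | birth weight, gestational age | malaria infection | No: neither |

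**3. Why the malaria-status RR cannot stand in.** Suppose infection multiplies LBW risk by m > 1 and treating detected infections does nothing. The by-arm RR is then 1, while the RR by PCR-defined status is m. Now suppose treatment removes all the excess risk in detected women, but detection is incomplete. The by-arm RR falls below 1, while the PCR-status RR stays above 1. The status RR does not show whether the strategy works.

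**4. Size of the parity omission.** The documents give no LBW rates by parity, so the ratio r of LBW in primigravidae to other women is assumed to be 1.5 to 3. The primigravida share, 13/34 = 0.382, is from Protocol Section 3 (phase 2 pilot). Women with second and later pregnancies are taken to share one risk.

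- LBW in other women: p_o = 0.1355/(1 + 0.382(r − 1)); in primigravidae: r × p_o.
- Between-strata share of variance: R² = 0.382 × 0.618 × (r·p_o − p_o)²/0.1171.
- SE overstatement when parity is ignored: 1/√(1 − R²) − 1.
- Actual alpha: 2[1 − Φ(1.960/√(1 − R²))].
- Adjusted power: Φ((1.960 + 0.842)/√(1 − R²) − 1.960).

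| r | LBW, others / primigravidae | R² | SE overstated | Actual alpha | Power after adjusting |
|---|---|---|---|---|---|
| 1.5 | 11.4% / 17.1% | 0.0065 | 0.3% | 4.9% | 80.3% |
| 3 | 7.7% / 23.0% | 0.0475 | 2.5% | 4.5% | 81.9% |

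**5. Can the data support the model?** After 20% attrition, 2583 × 0.8 ≈ 2066 women. At 3:1, expected LBW events are 517 × 0.173 + 1550 × 0.123 ≈ 280. Arm plus two parity terms gives 280/3 ≈ 93 events per term. Adding five centre terms for the six sites named in Protocol Section 5.1 gives 280/8 = 35.

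**The case against.** The strongest reply is that the comparison is already specified and only the model is missing. Superiority, ITT, two-sided 5% tests, 95% intervals and a final comparison of the arms are all in the SAP, and Protocol Section 5.8 adds the effect measure. That stands. A reader might infer from Section 6.2 that the trial plans no between-arm analysis of LBW, and the documents do not support that reading. But the protocol's sentence names no model or covariates, and it comes from v1.1. The SAP says "This document has been written based on information contained in the study protocol version 1.5", which is not among the supplied documents, so whether v1.5 says more cannot be checked.

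Other stronger readings also fail:

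- **Covariates picked freely by p-value.** Section 6.2 includes adjusters on an a priori hypothesised relationship, keeps those chosen on substantive grounds whatever the bivariate result, and limits all of them to documented risk factors. What remains is that screening is not excluded for the between-arm model.
- **Health centre as an ignored stratification factor.** Section 3.2 states stratification by parity only. Carrying out randomisation at each centre may or may not mean separate lists.
- **LBW denominator undefined.** Much of it can be inferred. SAP Section 6.1 places LBW within adverse livebirth and lists fetal loss separately, SAP Section 6.3 does not impute outcomes, and Protocol Section 5.8 excludes mothers of twins from birth-outcome analyses.
- **Malaria status undefined.** SAP Section 6.1 describes maternal malaria by any method and by each method. Section 6.2 only fails to say which definition its RR uses.

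**Conclusion.** The point holds as a gap in SAP Section 6.2, and it should be closed because it concerns the primary outcome. The section gives no analysis of LBW by randomised arm, and the birth-outcome RR it does specify addresses a different question from the one behind the 2583.

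The loss of precision is minor. Under the assumed 1.5- to 3-fold parity ratio, ignoring parity overstates the SE by 0.3–2.5%, with actual alpha 4.9–4.5%. An unadjusted by-arm RR would be valid and slightly conservative. A reader might infer that the trial's result would be biased, or that a status RR on the wrong side of 1 measures harm to it. The documents do not support either: the algebra in step 3 shows only that the two questions have different answers. As explanatory analyses, the malaria-status RR and the quantile regression are legitimate.

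**What to change.** In SAP Section 6.2:

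1. State the primary analysis as LBW by randomised arm (LAMP against standard of care) in the ITT population. Report the RR with 95% CI from a log-binomial model adjusted for the three parity strata, and for health centre if randomisation lists are kept by centre. Use modified Poisson with robust SE if the model does not converge.
2. Give the unadjusted RR as a sensitivity analysis.
3. State that bivariate p-value selection does not apply to this between-arm model.
4. Label the malaria-status RR and the quantile regression as secondary observational analyses, and say which definition of malaria status each uses.
5. Confirm the LBW denominator, which the documents suggest is singleton live births with a recorded weight.

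The cost is SAP wording and a few lines of code. Parity is already a baseline variable tabulated by arm (SAP Section 5.6), and centre is already used in summaries (SAP Section 5.1), so no new data and no change to the sample size are needed.
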